7.10.3.5 Other Exploratory Analyses

Relationships of sensitivity and specificity may be evaluated post-hoc with respect to additional covariates including, but not limited to, tumor size, tumor type, and tumor location.

7.11 Safety Endpoint Analyses

All the analyses in this section will be performed on the Safety population by Group. Patients will be analyzed according to the actual treatment they received.

Repeated or unscheduled results will not be included in the summary statistics but will be included in the individual data listings.

7.11.1 Adverse Events and Infusion Related Reactions

All adverse events (AEs) will be coded using the Medical Dictionary for Regulatory Activities (MedDRA). A TEAE is defined as an AE that occurs (or worsens) during or after study drug administration and through Day 28 after administration of study drug.

An overview of all AEs will be provided that will include:

- Number of AEs, TEAEs, non-serious TEAEs, and Serious Adverse Events (SAEs)
- Number of TEAEs and SAEs related to study drug
- Number of TEAEs related to study drug with CTCAE grade ≥ 3
- Number of AEs and study drug related SAEs resulting in:
 - Death

- Subject discontinuation
- Study drug discontinuation

TEAEs, treatment-related TEAEs, TEAEs by CTCAE grade, TEAEs that lead to discontinuation of study drug, SAEs, and SAEs that lead to discontinuation of study drug, will be summarized by system organ class (SOC) and preferred term (PT).

A listing of all AEs will also be generated.

Infusion related reactions (IRR) will be summarized, and a descriptive summary of the duration of IRR will be provided. A listing of all AEs, including a separate listing for IRR, will also be generated.

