2	18JAN2022	
• Updated the Medical Monitor• Updated the Project Manager• Included use of prophylactic diphenhydramine prior to pegsitacianine dosing• Removal of urinalysis, oral temperature, triglycerides, uric acid and iron tests• Corrected section numbering• Defined mucinous tumors as those that contain $\geq 50\%$ mucin• Updated “Day 10” follow-up visit to “Day 10 (± 5 days) or Day of Discharge (Whatever event occurs first)”• Updated safety information for the completed ON-1002 study• Corrected secondary endpoints• Removed hypothesis testing from sample size calculations• Updated the requirements to open Group 2 to enrollment• Removed Child-Pugh scores from exclusion criteria and restriction on use of investigational products 30 days prior to, and throughout the duration of the study• Included description of site personnel protocol training• Updated information on the intent to treat, efficacy and safety populations• Updated the statistical analysis to account for correlation
3	09SEP2022	
• Increased study enrollment size• Updated efficacy population definition• Updated sponsor contact

		
• Updated dosing window to 24-72 (± 8) hours• Clarified Screening Timing• Updated consumption of alcohol prior to surgery requirements• Updated imaging and/or biopsy inclusion wording• Updated wording on infusion rate• Update wording on day of surgery labs
--	--	------------------------------------------------------------------------------------------------------------------------------------------------------------------------------------------------------------------------------------------------------------------------------------------------------------------------------------------------------------------------------

TABLE OF CONTENTS

Signature Page	2
Table Of Contents	5
Protocol Summary	8
Abbreviations	14
1. Introduction.....	16
1.1 Overview	16
1.2 Pegsitacianine Clinical Trial Background.....	17
1.3 Pharmacodynamics and Dose Selection	18
2. Study Objectives	21
2.1 Primary Objective	21
2.2 Secondary Objectives.....	21
2.3 Exploratory Objectives	21
3. Study Plan	21
3.1 Overall Design	21
3.2 Imaging Assessments.....	22
3.3 Safety Assessments.....	22
4. Study Drug Dosage and Administration	22
4.1 Prohibited Medications and Restrictions	22
4.2 Study Drug Description	23
4.3 Study Drug Safety	23
4.4 Study Drug Packaging and Storage	25
4.5 Drug Accountability.....	25

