1. INTRODUCTION

1.1 Overview

Peritoneal carcinomatosis (PC) results from the metastasis of a primary cancer of the peritoneum (e.g., appendiceal, ovarian, uterine, colorectal, and gastric cancers) that then disseminates throughout the abdominal cavity.¹ Historically, progression to PC was considered terminal and resulted in survival times on the scale of a few months with palliative care being the best option for patients.² More recently, cytoreductive surgery (CS) has emerged as a means to prolong and improve patient lives with a median increase in survival of up to ~5 years.³ It has been reported that for every 10% increase in cytoreduction there is a 5.5% increase in median survival time.^{4,5} In addition to surgical tumor debulking within the peritoneal space, it has also been shown that coupling surgical intervention with hyperthermic intraperitoneal chemotherapy (HIPEC) can have an even greater impact on patient outcomes.⁶

The extent of survival benefit gained via CS is directly linked to the completeness of cytoreduction, or how much macroscopic disease (>2.5 mm deposits) has been removed.^{7,8} During CS, surgeons examine the peritoneal cavity for evidence of disease with the intent of removing all visible tumor deposits, and thus providing a complete cytoreduction. Any tumor deposits left behind, smaller than 2.5 mm, are believed to be treated efficiently with the follow-on HIPEC treatment.⁹ These surgical procedures are lengthy in duration, with total CS and HIPEC treatment times taking upwards of 14 hours to complete. Additional intraoperative tools for the identification of metastatic deposits may help to reduce total surgical time, as well as help identify disease that may be microscopic or unable to be detected with the naked eye (i.e., deep metastases). In an effort to aid surgeons in disease detection, focus has been placed on the development of fluorescent imaging agents that can accurately detect small deposits of disease that may be missed under standard white light surgical procedures.^{10,11}

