8.1 Definitions

The investigator is responsible for reporting all AEs that are observed or reported during the study, regardless of their relationship to study drug or their clinical significance.

An AE is defined as any untoward medical occurrence in a subject enrolled into this study regardless of its causal relationship to study treatment. Subjects will be instructed to contact the principal investigator if any symptoms develop.

A treatment-emergent AE (TEAE) is defined as any event not present before the first exposure to the study drug or any event already present that worsens in either intensity or frequency following the first exposure to the study drug.

All AEs that occur beginning on Day 0 must be reported in detail in the eCRF and followed to satisfactory resolution or until the principal investigator deems the event to be chronic or the subject to be stable. The description of the AE will include the onset date, duration, date of resolution, severity, seriousness, etiology, and the likelihood of relationship of the AE to study drug.

A serious adverse event (SAE) is defined as any event that results in any of the following outcomes:

- Results in death
- Is life threatening, i.e., the subject was, in the opinion of the investigator, at risk of death at the time of the event; it does not refer to an event that, hypothetically, might have caused death if it had occurred in a more severe form
- Requires inpatient hospitalization or prolongs existing hospitalization
- Results in persistent or significant disability and/or incapacity
- Is a congenital anomaly/birth defect
- Is an important medical event

Important medical events that may not result in death, be life threatening, or require hospitalization may be considered an SAE when, based upon appropriate medical judgment, they may jeopardize the subject and may require medical or surgical intervention to prevent one of the outcomes listed in this definition. Examples of such medical events include allergic bronchospasm requiring intensive treatment in an emergency room or at home, blood dyscrasias, convulsions that do not result in inpatient hospitalization, or the development of drug dependency or drug abuse.

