13. APPENDIX 1: SCHEDULE OF EVENTS (GROUPS 1 AND 2)

[figure not shown]
Evaluation	Screening	Treatment			
	Days -30 to 0	Day 0	Sur er postdose)	Day 10 (±5 days) or Day of Discharge	Day 28 (± 5 days)
Informed consent & subject enrollment	X				
Inclusion/exclusion criteria	X	X			
Blood/Urine/Breath alcohol		X			
Pregnancy test ^a	X	X			X
Demographic data	X				
Medical history	X				
Physical examination	X			X	
Karnofsky Performance Status	X				
Height ^b	X	X			
Body weight ^b	X	X			
Vital signs ^c	X	X	X ^d	X	X
12-lead electrocardiogram		X ^e		X	
Concomitant medications	X	X	X	X	X
Study drug administration		X ^f			
Adverse events review ^g		X	X	X	X
Serum chemistry	X	X	X	X	X
Hematology ^h	X	X	X	X	X
Surgery			X		
Intraoperative Imaging			X		
Pathology evaluation of surgical specimens			X ⁱ		

Footnotes

[figure not shown]
- ^a For female subjects, a serum sample for a serum pregnancy test will be collected at screening and on Day 0 and Day 28.
- ^b Body mass index will be calculated at Screening only.
- ^c Vital sign measurements will include systolic and diastolic blood pressure, pulse, respiratory rate, and temperature (in degrees Celsius). Blood pressure and pulse will be measured after a resting period of at least 5 minutes in the supine position.
- ^d Vitals are only to be collected if they are found to be abnormal at dosing
- ^e 12-lead ECG is to be performed prior to study drug administration
- ^f Prophylactic diphenhydramine may be administered prior to the administration of pegsitacianine
- ^g Patients will be assessed for AEs occurring from the time of dosing through Day 28 (± 5 days)
- ^h Hematology assessments will include hemoglobin, hematocrit, erythrocyte count (red blood cells), differential leukocytes, platelet count, and total leukocytes (white blood cells).
- ⁱ Pathologic analysis of surgical specimens will take place from the conclusion of surgery and up to 10 days after

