2. STUDY OBJECTIVES

2.1 Objectives and Endpoints

The main objective of this study is to investigate whether pegsitarcianine can detect residual disease in the peritoneal cavity following standard of care (SOC) resection of peritoneal metastases using a [REDACTED] mg/kg dose administered [REDACTED] prior to surgery.

Table 1. Objectives and Endpoints

Objectives	Endpoints
Primary Objective	Primary Endpoint

The primary objective of this study is to determine if administration of pegasitacianine (█ mg/kg) results in the detection of metastatic disease left behind following standard of care surgical resection of peritoneal metastases.
	
Rate of detection of disease left behind following SOC resection of peritoneal metastases as measured by rate of Clinically Significant Events (CSEs).

Secondary Objectives	Secondary Endpoints

Demonstrate reliable sensitivity, specificity, negative predictive values (NPPV), and positive predictive values (PPV) of the imaging agent at the level of the individual specimens.
	
Sensitivity, specificity, negative predictive values (NPV), and positive predictive values (PPV).

Demonstrate an acceptable safety profile.	Incidence of TEAEs and SAEs, abnormalities in lab values, vital signs, or ECG results.
Exploratory Objectives	Exploratory Endpoints
Assess the how the normalized SBR value affects the diagnostic accuracy of pegsitacianine in detection of metastatic disease vs. normal tissue.	ROC analysis across various specimen-to-background ratio fluorescence thresholds.
Effect of camera system on diagnostic results.	Diagnostic results across various camera systems.
Assess amount of fluorescence shown in various types of specimens.	Mean fluorescence intensity and Specimen-to-background ratio

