3. STUDY DESCRIPTION

3.1 Study Design

This Phase 2 study will be an interventional, open-label, single arm trial where each patient is his/her own “intrapatient” control using two Groups. All patients will receive a single █ mg/kg dose of pegsitacianine administered █ prior to standard of care surgery.

Patients enrolled in Group 1 of the study will have a biopsy confirmed diagnosis of non-mucinous peritoneal carcinomatosis, defined as less than 50% mucin in the sample, with a suspected Peritoneal Carcinomatosis Index (PCI) greater than or equal to 10. Group 2 of the study will include patients with a suspected PCI greater than or equal to 10 and a biopsy confirmed diagnosis of mucinous peritoneal carcinomatosis, defined as > 50% mucin in the sample. A total of approximately 60 patients will be enrolled across both Groups. Enrollment will be open first to Group 1 with the opportunity to open Group 2 for enrollment at the discretion of the sponsor.

In both Groups 1 and 2, the surgeon will perform their SOC resection of visible metastases and image each resected specimen, and normal specimens on an area of normal tissue outside of the surgical field using the intraoperative NIR camera; no NIR imaging of the peritoneal cavity will be performed at this time. At the conclusion of SOC resection, the intraoperative NIR camera will be used to investigate the peritoneal cavity further for evidence of residual metastases highlighted by fluorescence using an approach similar to that performed for the calculation of the Peritoneal Carcinomatosis Index (i.e., 13 regions). Additional fluorescent specimens will also be imaged on an area of normal tissue within the surgical field prior to sending all surgical specimens to pathology for examination. The fluorescence status of each specimen will then be directly correlated to the histopathological outcomes of each specimen. This study design enables the calculation of pgsitacianine sensitivity, specificity, NPV, and PPV. Additionally, Completeness of Cytoreduction (CC) scores can be calculated following SOC resection and then adjusted following the additional resection of fluorescent metastases. The schedule of events for this study is presented in [Appendix 1](#).

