4. SAMPLE SIZE AND POWER CALCULATION

The sample size for this study will be approximately 60 total subjects. This sample size is based on historical experience with similar pilot studies with the goal of informing power calculations for future studies. This study is not formally powered for hypothesis testing. A sample size of at least 40 total subjects (the originally planned sample size) will be sufficient for developing further understanding of the endpoints described herein. Sample size calculations account for non-evaluable and drop-out patients

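### The adverse event tables use one window from dosing through Day 28 that spans cytoreductive surgery, so all-cause incidence mixes drug and surgical events; a split at surgery would help

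*SAP*

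**What the plan says.** SAP Table 1 (section 2.1) measures the secondary objective of an acceptable safety profile by "Incidence of TEAEs and SAEs, abnormalities in lab values, vital signs, or ECG results". It sets no numerical criterion and makes no distinction by cause or by timing relative to surgery.

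SAP 7.11.1 defines a TEAE as an event that "occurs (or worsens) during or after study drug administration and through Day 28 after administration of study drug". It plans tables by system organ class and preferred term for TEAEs, treatment-related TEAEs, TEAEs by CTCAE grade, SAEs and events leading to discontinuation. Related SAEs and related TEAEs of grade 3 or higher appear as counts in an overview. Infusion-related reactions get their own summary, a summary of duration and a listing.

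Protocol 8.1 defines a TEAE as "any event not present before the first exposure to the study drug", or an existing one that worsens, with no reference to surgery. SAP 3.1 describes an "interventional, open-label, single arm trial where each patient is his/her own" control. Protocol 1.1, as general background, describes "total CS and HIPEC treatment times taking upwards of 14 hours to complete".

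The end of the window is stated in two ways. SAP 7.11.1 and the opening of Protocol section 8 say Day 28. Footnote g of Protocol Appendix 1 reads "Patients will be assessed for AEs occurring from the time of dosing through Day 28 (± 5 days", and footnote f of SAP Appendix 1 agrees with it.

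**The concern.** With no undosed arm, the interval between dosing and the start of surgery is the only part of follow-up in which an event cannot be a surgical complication. Pooling it with the postoperative weeks gives an all-cause incidence that depends on both the drug and the operation, and the two contributions cannot be recovered from the total. SAEs are affected directly, because Protocol 8.1 counts an event that prolongs a hospital stay as serious.

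The planned separation by cause helps only in part. Protocol 8.3 leaves causality to the investigator, who knows that every patient was dosed, and its middle category admits events with plausible timing that other factors could also explain. Many early postoperative events would fit that description. The infusion-reaction summary covers one event type, which the SAP does not define. Protocol 4.3 reports feeling cold as the commonest TEAE in the earlier Phase 2 study, and whether that would count as an infusion reaction here is not stated.

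At stake is how clearly a reader can judge the safety objective from the planned tables.

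**Working it through.** **Figures in the documents.** Protocol 4.3 gives TEAE incidence in the completed Phase 2 study as 26 of 30: 26/30 = 86.7%, matching the stated 87%. The current trial states no safety precision, threshold or power, so there is nothing else to reproduce. "The sample size for this study will be approximately 60 total subjects" (SAP section 4), and I use 60 below.

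**Share of the window before surgery.** The interval from dose to surgery is blacked out in the body. The only readable figure is the version-history entry "Updated dosing window to 24-72 (± 8) hours", taken here as an assumption: 24 − 8 = 16 h to 72 + 8 = 80 h. The window is 28 × 24 = 672 h. 16/672 = 2.4% and 80/672 = 11.9%, so at least 88% of the window is during or after surgery. This describes exposure time only. It does not measure how many events are misattributed.

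**Dilution.** Let d be the risk of a drug event before surgery and s the risk of any event due to surgery. If the two are independent:

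- overall incidence = 1 − (1 − d)(1 − s)
- rise over surgery alone = d(1 − s)

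For d I use one third, the infusion-reaction frequency in Protocol 4.3, as an illustrative size. The documents give no value for s, so a range is shown.

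| Assumed s | Overall incidence with d = 1/3 | Rise over s |
|---|---|---|
| 30% | 1 − 0.667 × 0.70 = 53.3% | 23.3 points |
| 50% | 1 − 0.667 × 0.50 = 66.7% | 16.7 points |
| 80% | 1 − 0.667 × 0.20 = 86.7% | 6.7 points |
| 95% | 1 − 0.667 × 0.05 = 96.7% | 1.7 points |

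Measured before surgery, the same drug rate reads 33 points. A positive association between drug and surgical events would shrink the rise further.

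**Anchor for s.** If the earlier study's 86.7% is combined with d = 1/3, then s = 1 − (1 − 0.867)/(2/3) = 80%. This is only an anchor: tumors and operations differed, and the text available does not split those TEAEs by cause.

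**What a split would show.** With 60 treated patients and both Groups pooled (exact 95% intervals):

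- Before surgery: d = 1/3 gives 20/60 = 33% (22 to 47%), and d = 2/3 gives 40/60 = 67% (53 to 78%). The intervals do not overlap.
- Unsplit, with s = 80%: the same two rates give 52/60 = 87% (75 to 94%) and 56/60 = 93% (84 to 98%). The intervals overlap heavily.

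**Window end.** A Day 28 visit may fall as late as Day 33. An event starting on Days 29 to 33 would be collected under the schedule footnotes but would not be a TEAE under SAP 7.11.1.

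**The case against.** The best reply is that events are unsplit by time, not by cause. SAP 7.11.1 already isolates treatment-related TEAEs and infusion reactions. The one-third rate used above is itself an infusion-reaction rate; Protocol 4.3 says these generally begin within 5 minutes of infusion start, and a rise in them would show in their own summary. That stands: the dilution figures describe all-cause incidence, and the practical gain is for early drug events not classed as infusion reactions and for the SAE and grade tables.

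A reader might infer that surgical morbidity swamps the drug signal, or that the safety objective cannot be judged at all. The documents do not support either. They give no surgery-only rate. Dilution is moderate at an assumed 30 to 50% and severe only towards 95%. Protocol 1.1 discusses HIPEC as background and does not say how many participants receive it.

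A reader might also infer that laboratory results are pooled across surgery. They are not: the day of surgery is a scheduled sample (Protocol 7.6), and SAP 7.11.2 summarizes results by scheduled time point with change from baseline.

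The Day 28 mismatch is minor. Protocol section 8 also says Day 28, and the listing of all adverse events would still show a later one.

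Finally, safety is a descriptive secondary objective in an unpowered pilot, and table layout is left to a separate document that is not available here.

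**Conclusion.** The point holds as a reporting gap. The named safety endpoint is all-cause incidence over one window that contains major surgery, there is no comparator, and neither document plans an adverse event table split at surgery. Related TEAEs and infusion reactions fill the gap only in part, for the reasons given above.

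The size depends on an unknown. A one-third drug event rate before surgery would add about 23 points to overall incidence if surgery alone causes events in 30% of patients, 17 at 50%, 7 at 80% and 2 at 95%. This assumes independence and an illustrative drug rate. No stated figure is wrong, and the primary endpoint is not affected. I would class it as a change to consider.

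**What to change.** In SAP 7.11.1, present the TEAE, SAE and CTCAE-grade tables by onset period (dosing to start of surgery; start of surgery to the Day 28 visit) plus the total. State that the safety conclusion will be read from the pre-surgical period together with related TEAEs, related SAEs and infusion reactions, with all-cause incidence as context.

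Reconcile the end of the TEAE window across SAP 7.11.1, Protocol section 8 and both schedule footnotes, so that every collected event is classified in the same way. No change to the laboratory analysis is needed.

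The cost is SAP wording, which SAP 7.1 allows to be updated before database lock, and longer tables. Protocol 8.2 already collects time of onset, although 8.1 asks only for the date; events on the day of surgery will need the time. SAP 7.9.5 lists duration of surgery but not its start, so confirm that the start time is captured. The split will not separate drug effects that first appear after surgery; only a comparator could do that.

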6.4 Early Withdrawal Procedures

If a subject is withdrawn from the study before study completion, all procedures scheduled for the final visit (Day 28 ± 5 days) should be performed if possible.

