8. REPORTING ADVERSE EVENTS

All adverse events (AEs) will be recorded in the eCRF, whether they are observed by the investigator, reported by the subject, observed from laboratory findings, or collected by other means. Adverse events will be monitored beginning on Day 0 through the end of the study (Day 28). Adverse events will be graded by the Investigator using a numerical score according to the defined National Cancer Institute Common Terminology Criteria for Adverse Events (NCI CTCAE) Version 5.0 (2017).

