8. DEVIATIONS FROM ANALYSIS AS DESCRIBED IN THE PROTOCOL

No deviations from the protocol are planned.

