24 JAN 2023

- ^a For female subjects, a serum sample for a serum pregnancy test will be collected at screening and on Day 0 and Day 28.
- ^b Body mass index will be calculated at Screening only.
- ^c Vital sign measurements will include systolic and diastolic blood pressure, pulse, respiratory rate, and oral temperature (in degrees Celsius). Blood pressure and pulse will be measured after a resting period of at least 5 minutes in the supine position.
- ^d Vitals are only to be collected if they are found to be abnormal at dosing
- ^e 12-lead ECG is to be performed prior to study drug administration
- ^f Patients will be assessed for AEs occurring from the time of dosing through Day 28 (± 5 days)
- ^g Hematology assessments will include hemoglobin, hematocrit, erythrocyte count (red blood cells), differential leukocytes, platelet count, and total leukocytes (white blood cells).
- ^h Pathologic analysis of surgical specimens will take place from the conclusion of surgery and up to 10 days after

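### The SAP's TEAE window stops at Day 28 with no visit allowance, while adverse events are collected to a final visit that may fall on Day 33; the two should be aligned

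*SAP*

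**What the plan says.** Five places bear on when an adverse event stops counting as treatment-emergent.

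- **SAP 7.11.1** defines a TEAE as an event that "occurs (or worsens) during or after study drug administration and through Day 28 after administration of study drug". No ± window is attached.
- **SAP Appendix 1, footnote f**, and in the same words **Protocol Appendix 1, footnote g**: "Patients will be assessed for AEs occurring from the time of dosing through Day 28 (± 5 days").
- **Protocol 6.4**, on early withdrawal, confirms the window of the last visit: "all procedures scheduled for the final visit (Day 28 ± 5 days) should be performed if possible".
- **Protocol 8.1** defines a TEAE as "any event not present before the first exposure to the study drug or any event already present that worsens" after first exposure. It names no last day.
- **Protocol section 8**, opening paragraph: "Adverse events will be monitored beginning on Day 0 through the end of the study (Day 28"). Here the visit window is missing.

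Two further statements settle which text governs. SAP section 1 gives the SAP precedence over the protocol for analysis and reporting. SAP section 8 states: "No deviations from the protocol are planned".

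**The concern.** The SAP's classification rule can end before the SAP's own collection period does. A patient may attend the last visit within its permitted window and report a new event that is validly recorded but, on a literal reading, is not treatment-emergent.

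Scheduled data are affected as well as chance late reports. Blood is drawn and vital signs are taken at the Day 28 (± 5 days) visit, and Protocol section 8 requires adverse events found from laboratory results to be recorded. A laboratory abnormality first found and dated at a Day 27 visit would be a TEAE; the same finding at a Day 31 visit would not. Classification would then depend on the appointment date and not on the event.

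TEAE incidence is one of the safety endpoints in SAP Table 1, next to SAE incidence and laboratory, vital-sign and ECG abnormalities. A cut-off that is too early can only lower the TEAE figures. The SAE outputs carry no such cut-off, so the two sets of tables could disagree for the same patient.

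**Working it through.** The plan gives no figure to reproduce. The check is day arithmetic on its own windows, followed by a reading of which outputs depend on the TEAE flag.

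**Inputs**
- TEAE limit: Day 28 after administration (SAP 7.11.1).
- Adverse event collection: dosing through Day 28 ± 5 (footnote f of SAP Appendix 1; footnote g of Protocol Appendix 1).

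**Step 1. Range of the final visit.** Earliest 28 − 5 = Day 23; latest 28 + 5 = Day 33.

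**Step 2. Collected days outside the TEAE window.** For a final visit on day v, uncovered days = max(0, v − 28). The share of that patient's collection period, counting Day 0, is uncovered days / (v + 1).

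| Final visit (day v) | Uncovered days | Share of collection days |
|---|---|---|
| 23 to 28 | 0 | 0% |
| 29 | 1 | 1/30 = 3.3% |
| 30 | 2 | 2/31 = 6.5% |
| 31 | 3 | 3/32 = 9.4% |
| 32 | 4 | 4/33 = 12.1% |
| 33 | 5 | 5/34 = 14.7% |

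The gap is therefore Days 29 to 33 at most, and it exists only for patients seen after Day 28.

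**Step 3. Outputs in SAP 7.11.1 that would miss such an event.** These are the TEAE and non-serious TEAE counts, the related-TEAE count, the count of related TEAEs of grade 3 or higher, and the system organ class and preferred term summaries of TEAEs, related TEAEs and TEAEs by grade. The summary of TEAEs leading to discontinuation of study drug is also tied to the flag, but with one dose on Day 0 a late event can hardly lead to discontinuation.

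**Step 4. Outputs that would keep it.** These are the count of all AEs, the SAE and related-SAE counts, the SAE summary by system organ class and preferred term, and the listing of all AEs. None is restricted to TEAEs.

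**Step 5. Consequence.** An SAE with onset on Day 30 would be in the SAE table and absent from the TEAE table. A non-serious event with onset on Day 30 would be in the all-AE count and the listing, but in no summary by preferred term or grade.

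**Step 6. After the change.** With the TEAE window run to the final visit, uncovered days are 0 for every v from 23 to 33.

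**The case against.** **Day 28 may mean the visit.** Both documents use Day 28 as a visit label without its window: Protocol 7.4, 7.6 and 7.6.1 do so, and so does the column head of the SAP schedule. The protocol's own visit heading (6.3) places the ± 5 days between the label and the reference to dosing, so the SAP wording could be a shortened form of it. On that reading nothing is lost. This stands as a plausible intention. But the SAP sentence, as it is written, counts days from administration, and a programmer could reasonably code dose date plus 28. If the visit was meant, the edit merely records it.

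**The SAP agrees with Protocol section 8.** That paragraph bounds monitoring at Day 28. A reader who compares only SAP 7.11.1 with Protocol 8.1 might infer that the SAP departs from the protocol while declaring no deviation. The documents do not support that firmly, because the protocol is itself inconsistent: section 8 omits the window, Appendix 1 includes it, and 8.1 gives no end. The firmer conflict lies inside the SAP, between 7.11.1 and footnote f.

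**Late events are not lost.** This is correct, as Step 4 shows. In particular, a late event that requires or prolongs hospitalization is an SAE under Protocol 8.1 and stays in the SAE tables. A reader might infer that serious late post-operative events would be hidden from the report; they would not be.

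**A fixed window treats patients alike.** It does so only in part. Patients seen on Days 23 to 27 already have a shorter collection period, so a Day 28 limit leaves unequal periods and truncates only those seen late.

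**Conclusion.** The point holds as an inconsistency with a limited reach. Coded literally, SAP 7.11.1 leaves up to 5 collected days (Days 29 to 33) outside the TEAE summaries for patients whose final visit falls after Day 28. All-AE counts, SAE outputs and listings are unaffected, so the visible symptom may be SAE and TEAE tables that do not reconcile.

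The size in events cannot be computed: neither document gives a late adverse event rate or a distribution of final visit days. The effect is probably small. There is a single dose, and Protocol 4.3 describes the most common anticipated related events as infusion reactions, generally starting within 5 minutes of infusion start.

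A reader might put a larger number on it. If final visits were spread evenly over Days 23 to 33, 5 of 11 visit days would fall after Day 28, and 5/11 × 60 is about 27 patients. The documents do not support that figure. The even spread is an assumption with no basis in them, it takes all 60 patients to the last visit although the sample size allows for drop-outs, and it counts patients with uncovered days, not events. Even on that assumption the average over all patients is (1 + 2 + 3 + 4 + 5)/11 = 1.4 days. That late visits belong to sicker patients is likewise only a possibility.

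The conclusion rests on the calendar reading of the SAP sentence. Under the visit reading, only the wording needs repair.

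**What to change.** In SAP 7.11.1, define a TEAE as an adverse event with onset or worsening from the start of study drug administration through the patient's final study visit (Day 28 ± 5 days). That agrees with footnote f and with the protocol schedule. Align Protocol section 8 by adding the same window to its statement of when monitoring ends. If a calendar limit at Day 28 is truly intended, state it as such, give the reason, and record it in SAP section 8.

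The cost is one SAP sentence, one programming cut-off and a short wording change in the protocol. SAP 7.1 allows updates before database lock, so the SAP edit should be made by then. TEAE counts may rise slightly, and the TEAE observation period will follow each patient's visit date, from 23 to 33 days, where a literal Day 28 limit would give 23 to 28.
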